
STATISTICS Primary Analysis Plan
	
[name] has expertise in epidemiology and biostatistics. Differences in residual viral transcription by MA exposure will be evaluated using multivariate negative binomial regression, as previously described. Potential covariates will include age, gender, nadir CD4+ T cell count, pre-ART HIV RNA, recent CD4+ T cell count, timing of ART (estimated date of HIV infection to date of ART initiation), duration of ART suppression, and other illicit use (stimulant or opioid exposure detected on qualitative urine measurement). Linear regressions will be used to associate MA concentrations with urinary \square-PEA levels. For the RNA sequencing data, within-individual differential gene expression analyses will be performed for each tissue type (blood and lymph node) and for each cell type (Tcm CD4+ T cells or CD14+ monocytes). Deconvolution of cell-specific gene signatures⁶⁹ will be performed to allow analysis of further cell subsets (e.g., “classical” vs. “non-classical” monocytes). For DNA variant analyses, SNP-based association tests between variants and TAAR1 signaling biomarkers will be performed using PLINK/SEQ, while gene-based association tests will be performed using SKAT-O, which aggregates variants across a region and assesses whether the number of variants with non-zero effect sizes within that region exceeds that of chance expectation. Genes and pathways will be filtered for those associated with changes in viral transcription using several pathway sources - e.g., Ingenuity Pathway Analysis (IPA), KEGG, MsigDB (Broad), and Damian Chaussabel’s immune modules. Functional Annotate Network (FAN) will be built using Genes2FANs and Cytoscape to show the key functional network elements that are downstream of candidate genes. String (string-db.org) will be used to build protein-protein interaction networks from the differentially expressed gene lists. Finally, graph theory analysis will be used to identify the functional motifs of the network.

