2.1 Risk / Benefit Assessment

Side effects associated with taking the study medication

Likely to occur:

- Oral methamphetamine is a stimulant and may cause increased blood pressure, heart rate, and palpitations (noticeably rapid, strong, or irregular heartbeats).

Less likely to occur:

- In some cases, oral methamphetamine can cause some dizziness, headache, insomnia, elevated mood, depressed mood, restlessness, diarrhea, constipation, unpleasant taste, dry mouth, and tremor (hands shaking).

Very unlikely to occur:

- At very high doses (much higher than the doses being given in this study) and if taken for prolonged periods of time (e.g., weeks to months to years), oral methamphetamine can lead to a substance use disorder, exacerbation of preexisting abnormal movements (called “tics”), psychotic symptoms (hearing and seeing things that are not actually there), frequent erections, impotence, and changes in libido.

Side effects associated with taking placebo

Very unlikely to occur:

- In order to make the placebo appear similar to the study medication, the pills will be crushed and placed in a capsule. For the placebo phase, cornstarch will be placed inside the capsule. Therefore, individuals who have an allergy to cornstarch may be at risk of an allergic reaction when taking placebo and should notify the study investigator if they have a known allergy to cornstarch.

HIV viral load and resistance to antiretroviral therapy risks

Very unlikely to occur:

- We will be measuring the amount of viral RNA that increases after the study drug. This does not necessarily mean that there is an increase in the amount of circulating HIV. Nonetheless, since there is a very small chance that there could be an in circulating virus, there would be a theoretical risk of developing resistance to antiretroviral therapy. The likelihood of this is extremely low, given that participants will only be given one day of a single day's maximum pediatric dose of the study medication, and if the study medication induces viral rebound, the predicted increases in HIV in the blood is extremely small. For these reasons, individuals can only participate in this study if there are alternate ART regimens available in the rare event that their current ART regimen is compromised as a result of this study. During the study, participants will have their HIV viral load followed closely (at screening, baseline, and on days 2, and 31 of each treatment arm).

Drug-drug interactions

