4 STUDY DESIGN

4.1 Study Overview

This is a phase IV open label randomized, double-blinded, placebo-controlled crossover study. A placebo treatment arm will be assigned to participants in a randomized crossover design. HIV+ ART-suppressed individuals with no prior history of MA use disorder will be administered 10mg oral methamphetamine hydrochloride (Desoxyn®), followed by 15 mg methamphetamine hydrochloride two hours later, for a total of 25mg in one 24-hour period (the maximum FDA approved daily dose for the treatment of childhood obesity). Participants will complete the study twice (once on a placebo treatment arm and once with the Desoxyn® treatment arm). Which treatment arm occurs first will be randomly assigned and will include a 31-day washout period between the two phases. The placebo is similar in appearance, consistency, and taste to methamphetamine hydrochloride tablets, USP (Desoxyn®), without any known drug-drug interactions (e.g., changes in pH balance that might affect drug absorption) with HIV antiretroviral therapy.

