8 STUDY TREATMENTS

8.1 Method of Assigning Participants to Treatment Groups

Participants will be randomized to either oral methamphetamine versus placebo treatment first using a random number generator. Whichever treatment the participant receives first, they will receive the other treatment (placebo or oral methamphetamine) for their second treatment phase starting at Day 77 (See Study Events Table in Other Documents).

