14.3 Analysis of Primary Endpoint

Paired analyses using Wilcoxon signed rank tests will be performed to evaluate whether there is a statistically significant change in markers of immune activation (e.g., CD69, CD38, and/or HLA-DR) on CD4+ and CD8+ T cells, as well as log-transformed levels of plasma cytokines (e.g., IL-6, IL-1b, IFN- γ) after study drug compared to baseline (reference will be the average of the three baseline measures). Multivariate analyses will then be performed to evaluate the association between study drug and measures of immune activation at post-dosing, using linear mixed effects models, which account for within-participant correlation of observations and allows for greater stability in the estimate of the outcome measures within individuals. Similarly, for measures of the HIV transcription, linear mixed effects regression to compare CA-US RNA levels before and after study drug will be performed. Negative binomial mixed effects regression (a method to analyze over-dispersed count data) to compare plasma HIV RNA levels before and after study drug administration (reference will be the average of three baseline measures).

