14.5 Sample Size

Assuming a log normal distribution of HIV-1 cell-associated (CA)-US RNA and a standard deviation of 0.6 log₁₀ copies/10⁶ CD4+ T cells (as above for Aim 1125), with 10 participants in the treatment arm, and a null hypothesis of no change in CA-US RNA, we estimate that the study will have approximately 80% power to detect a 0.5-0.6 log₁₀ difference in CA-US RNA before and after treatment peak, at the 0.05 significance level. For the gene expression analyses, assuming a coefficient of variation of 0.32 and approximately 80-90% sequencing depth between 5 to 8 copies per base, respectively, we estimate having greater than 80% power to detect a two-fold change at the 0.05 significance level.

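### The HIV transcription outcome is analysed and powered as a before/after change; the methamphetamine-minus-placebo contrast that the randomised crossover provides is never specified

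*Combined protocol and SAP*

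**What the plan says.** Section 4.1 sets up the control: "A placebo treatment arm will be assigned to participants in a randomized crossover design". Section 8.1 confirms that everyone gets both treatments: "Whichever treatment the participant receives first, they will receive the other treatment (placebo or oral methamphetamine) for their second treatment phase".

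The statistical text does not follow that design through:

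- **Section 14.3, HIV transcription:** "linear mixed effects regression to compare CA-US RNA levels before and after study drug will be performed". Plasma HIV RNA is also compared before and after dosing, and the Wilcoxon tests on immune markers and cytokines compare post-dose values with baseline. The only reference value stated, given for the markers, cytokines and plasma HIV RNA, is the mean of three baseline measures.
- **Section 14.3, immune activation:** a mixed model is to "evaluate the association between study drug and measures of immune activation at post-dosing". This implies a drug contrast but names no comparator.
- **Synopsis (Primary Analysis Plan) and section 14.4 (secondary endpoints):** "Differences in residual viral transcription by MA exposure will be evaluated using multivariate negative binomial regression". The same sentence is primary in one place and secondary in the other.
- **Section 14.5 and the synopsis sample-size row:** about 80% power for a 0.5 to 0.6 log10 "difference in CA-US RNA before and after treatment peak, at the 0.05 significance level", with 10 treated participants, SD 0.6 log10 and a null of no change.

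Placebo is not mentioned in section 14 or in the synopsis statistics rows. Neither contains a period, sequence or carryover term.

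**The concern.** The primary objective is causal: whether short-term methamphetamine exposure raises residual viral production. A before/after comparison in the methamphetamine phase cannot separate the drug from whatever else differs between baseline and post-dose, such as assay drift, time of day, repeated blood draws or natural fluctuation in transcription. The placebo phase exists to make that separation, but the plan does not say how it enters the CA-US RNA analysis.

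It is also unclear which analysis of HIV transcription is primary: the before/after mixed model of section 14.3, or the exposure regression that the synopsis calls primary and section 14.4 calls secondary. That leaves room to choose after the results are known.

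**Working it through.** **Inputs.** From section 14.5: n = 10, SD 0.6 log10, significance level 0.05, differences of 0.5 to 0.6 log10. Assumed because the plan is silent: a two-sided test; 0.6 is the SD of one participant's before/after change; the correlation r between a participant's two changes is 0, 0.25, 0.5 or 0.7; five participants per sequence; non-drug shifts of 0.1, 0.2 and 0.3 log10.

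**1. Reproduce the plan's figure.** One-group paired t-test, df = 9, SE = 0.6/√10 = 0.190, noncentrality = difference/SE.

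- 0.5 log10: 0.5/0.190 = 2.64, power 65%.
- 0.6 log10: 0.6/0.190 = 3.16, power 80%.
- Difference detectable with 80% power: 0.60 log10.

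The stated figure is recovered as a single-group before/after test, at the upper end of its range. An unpaired comparison of 10 against 10 gives only 42% to 56%, so the plan did not power methamphetamine against placebo in that form.

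**2. False positives when the drug does nothing.** Same test, with the non-drug shift in place of the drug effect:

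| Assumed shift (log10) | Noncentrality | Before/after test significant | Period-adjusted contrast significant |
|---|---|---|---|
| 0.1 | 0.53 | 7.6% | 5% |
| 0.2 | 1.05 | 15.7% | 5% |
| 0.3 | 1.58 | 29.3% | 5% |

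The contrast stays at 5% because a shift common to both phases cancels. A simulation of 200,000 trials with the same shift in both phases, at r = 0 and r = 0.5, gave 4.9% to 5.0% for the contrast and matched the before/after column to within 0.2 percentage points.

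**3. Power of the crossover contrast.** For each participant, D = methamphetamine change minus placebo change. SD(D) = 0.6 × √(2(1 − r)), SE = SD(D)/√10, and df = 8 after adjusting for period.

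| r | SD(D) | Power at 0.5 | Power at 0.6 | Detectable with 80% power | Even n for 80% power at 0.6 |
|---|---|---|---|---|---|
| 0 | 0.849 | 38% | 50% | 0.86 | 18 |
| 0.25 | 0.735 | 47% | 62% | 0.74 | 14 |
| 0.5 | 0.600 | 64% | 79% | 0.61 | 12 |
| 0.7 | 0.465 | 85% | 95% | 0.47 | 8 |

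With n = 10, 80% power needs r of about 0.51 for 0.6 log10 and about 0.66 for 0.5 log10.

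**4. Check of the proposed model.** The variance of the treatment-by-time coefficient in the mixed model recommended below is 2 × 0.6² × (1 − r)/10. This equals SD(D)²/10 from step 3, so the table applies to that model.

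**The case against.** The best counter-argument is that the comparator is implied. The immune-activation model in section 14.3 uses post-dose data, where the only thing that varies within a person is methamphetamine or placebo. The CA-US RNA sentence then opens with the word similarly, which ties it to that model. Since non-study methamphetamine use is excluded, exposure in section 14.4 can differ only by phase or by time. If before/after changes were reported for both phases, the placebo change would at least be visible. This softens the point, but the CA-US RNA sentence still specifies a before/after comparison, and the power statement tests exactly that. The exposure regression names no comparator or pairing, and its listed covariates are nearly all fixed within a person. It relies on a cited method that cannot be judged from the documents.

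The size is also open to challenge. The shifts are assumed, and 0.6 could be the SD of a single level. On that reading, with equal correlations of 0.5, 0.75 or 0.9 among all measures, SD(D) is 0.6 × √(4(1 − correlation)) = 0.85, 0.60 or 0.38, and power at 0.6 log10 is 50%, 79% or 99%. This largely overlaps the range above. A five/five split is not guaranteed either: section 8.1 mentions only a random number generator, and simple randomisation gives that split about 25% of the time (252/1024). At r = 0.5, a three/seven split lowers 79% to about 72%. These objections change the numbers but do not supply the missing contrast.

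Finally, section 5.1 says there is no primary efficacy endpoint, which suggests a modest mechanistic study. But the synopsis names HIV virus replication as primary and section 14.3 is headed as its analysis, so that conflict also needs resolving.

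**Conclusion.** The concern holds and should be fixed before unblinding. As written, the analysis and power of the HIV transcription outcome do not use the randomised control. The specification gap follows from the text alone and depends on no assumption.

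Its consequence depends on the size of any non-drug shift, which the documents do not give: about 8% to 29% false positives for 0.1 to 0.3 log10, taking 0.6 as the SD of a change. Whether 10 participants suffice for the proper contrast cannot be settled from the plan, because neither the meaning of the 0.6 nor the correlation is stated. Under the readings shown, power at 0.6 log10 runs from about 50% to 95% or more.

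**What to change.** **Section 14.3.** Name one primary analysis: the methamphetamine-minus-placebo difference in change in log10 CA-US RNA from each phase's own baseline.

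- Fit a linear mixed model with fixed effects for treatment, time, treatment-by-time, period and period-by-time, and random effects for participant, participant-by-period and participant-by-time. Test treatment-by-time.
- State the fallback in advance, since the model may not converge with 10 people: regress each participant's D on sequence coded +1/−1 and test the intercept on 8 df. With complete data this gives the same estimate, so it could also be the primary method outright.
- Run the Wilcoxon tests on methamphetamine change minus placebo change.
- Add treatment-by-time to the plasma HIV RNA model, and name placebo as comparator in the immune-activation model.
- Keep before/after changes as descriptive results.

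**Synopsis, sections 5.1 and 14.4.** Make them name the same primary endpoint and analysis as section 14.3.

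**Section 14.5 and the synopsis sample-size row.** Restate the power for this contrast, giving the assumed SD of change, the correlation and the allocation to sequences.

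**Cost.** Rewording only. Both phases are already run, and plasma viral load is already scheduled: "participants will have their HIV viral load followed closely (at screening, baseline, and on days 2, and 31 of each treatment arm". CA-US RNA sampling times are in a Study Events Table that was not available, so this assumes that both phases are sampled alike, each with its own baseline. The downside is that the stated power falls if r is below about 0.5. In that case, either a larger detectable difference must be accepted or the sample increased, to about 14 participants at r = 0.25 or 18 at r = 0 for 0.6 log10.

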6.2 Inclusion Criteria

2. Willing and able to provide written informed consent
3. Male or female, age ≥ 18 years and ≤ 65 years
4. Laboratory confirmed documentation of HIV-1 infection.
5. Continuous therapy with a DHHS recommended/alternative combination ART for least 12 months (at least 3 agents) at study entry with no regimen changes in the preceding 12 weeks
6. Maintenance of undetectable plasma HIV-1 RNA below the limit of quantification for at least 12 months. Episodes of single HIV plasma RNA 50-500 copies/ml will not exclude participation if subsequent HIV plasma RNA is below the limit of assay detection.
7. No plans to modify ART during the study period (146 days, or approximately 5 months)
8. Participant and partner(s) are willing to use two forms of contraception throughout the study period as well as up to 60 days after the last day of study completion.
9. Ability and availability to participate in the full 146 days of the study (approximately 5 month) and maintain the inclusion/exclusion criteria
10. No current or prior history of methamphetamine (MA) use disorder by DSM-5 diagnostic criteria. Participants may have a prior history of taking prescription

medications containing amphetamines-type stimulants such as Adderall® or Dexedrine® or Ritalin for the treatment of conditions such as attention deficit hyperactivity disorder as long as the participant has not taken these medications in the last 12 months or plans to take these medications during the entire study period.

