9.3 Research Laboratory Measurements

9.3.1 HIV Clinical Laboratory Assay Measures

Blood will be obtained and sent to San Francisco General Hospital clinical laboratory for real-time determination of CD4+ and CD8+ T cell counts and plasma HIV RNA (viral load).

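### The negative binomial model for plasma HIV RNA needs a number for every non-detect, no rule supplies one, and the choice largely sets the estimated ratio

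*Combined protocol and SAP*

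**What the plan says.** Section 14.3 gives the two virologic measures different models. For cell-associated RNA, "linear mixed effects regression to compare CA-US RNA levels before and after study drug will be performed". For plasma it plans "Negative binomial mixed effects regression (a method to analyze over-dispersed count data) to compare plasma HIV RNA levels before and after study drug administration", where the "reference will be the average of three baseline measures".

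Four other places determine what the plasma data will look like:

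- **Eligibility (6.2, same in the synopsis):** "Maintenance of undetectable plasma HIV-1 RNA below the limit of quantification for at least 12 months". The criterion goes on: "Episodes of single HIV plasma RNA 50-500 copies/ml will not exclude participation", provided the next value is below the limit of detection.
- **Assay (9.3.1 and 9.3.2):** plasma HIV RNA is measured as the hospital laboratory's viral load. The research virology assays are cell-associated unspliced and multiply spliced RNA and 2-LTR DNA. No low-copy plasma assay is described.
- **Expected effect (2.1):** should the drug induce rebound, "the predicted increases in HIV in the blood is extremely small".
- **Timing (2.1):** viral load is followed "at screening, baseline, and on days 2, and 31 of each treatment arm".

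The documents give no plasma limit of quantification, no rule for non-detects, no censored-data method and no plasma-volume offset.

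**The concern.** A viral load reported as below the limit is a left-censored measurement. It is not a count, and it is not a number. A negative binomial likelihood cannot take it as it stands, and neither can a three-value mean. Because 14.3 names both and says nothing about non-detects, someone must pick a value for each one, possibly after the data are in hand. If most observations are non-detects, that value makes up most of the data.

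What is at stake is the reported ratio of plasma HIV RNA after study drug to before it. The same samples could give a ratio close to 1, a large ratio, or a fit that does not converge. A reader could not tell how much of the result came from the virus and how much from the substitute.

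**Working it through.** **1. The plan's own figure.** Section 14.5 states about 80% power for a 0.5-0.6 log10 change in CA-US RNA with n = 10, SD 0.6 and alpha 0.05. Take the SD as that of the within-person change and use a two-sided paired t test on 9 df, with noncentrality δ√n/σ.

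- δ = 0.6: 0.6 × √10 / 0.6 = 3.16, power 0.803.
- δ = 0.5: 0.5 × √10 / 0.6 = 2.64, power 0.651.

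The difference detectable at 80% power is 0.598 (two-sided t), 0.532 (two-sided normal) or 0.512 (one-sided t), so the figure reproduces. It concerns CA-US RNA only. No power is given for plasma HIV RNA.

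**2. Dependence on the substitute, by arithmetic.** Ignoring the random effect, a log-link count model estimates a ratio of means. Take 10 participants with three baselines and one post-dose value each. Let s be the substitute, v the quantifiable value, and k_b and k_p the numbers quantifiable before and after:

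ratio = {[(10 − k_p)s + k_p·v]/10} ÷ {[(30 − k_b)s + k_b·v]/30}

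The limit is not in the documents; 40 copies/ml is assumed here, with v = 60.

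| Quantifiable (base, post) | s = 0 | s = 1 | s = 20 | s = 40 |
|---|---|---|---|---|
| 0/30, 2/10 | infinite | 12.8 | 1.40 | 1.10 |
| 1/30, 2/10 | 6.0 | 4.3 | 1.31 | 1.08 |

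For example, row 1 with s = 20 is (8 × 20 + 2 × 60)/10 = 28, and 28/20 = 1.40. For row 2, the ratio from s = 0 to s = limit runs from 6.0 to 1.31 if the limit is 20, and from 6.0 to 1.03 if it is 50.

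One case is free of the limit L: all baselines below L and one of ten post-dose values at 1.5L. The ratio is (9s + 1.5L)/(10s), which is 1.05 at s = L, 1.20 at s = L/2, and a division by zero at s = 0. If every value is below the limit, the ratio is 1 for any positive constant and undefined at zero.

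**3. Dependence on the substitute, with the mixed model fitted.** A negative binomial random-intercept model was fitted to 150 simulated data sets per scenario. Assumptions: limit 40, lognormal true values, between- and within-person SD 0.4 log10 each, about 5% of baseline values quantifiable.

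| True ratio (post-dose quantifiable) | Result | s = 0 | s = 1 | s = 20 | s = 40 |
|---|---|---|---|---|---|
| 1 (4%) | median ratio | 0 (degenerate) | 1.0 | 1.0 | 1.0 |
| | share with p < 0.05 | 6% | 10% | 5% | 1% |
| 3 (21%) | median ratio | about 38 | 3.2 | 1.38 | 1.17 |
| | share with p < 0.05 | 27% | 58% | 60% | 50% |
| 6 (39%) | median ratio | at fitting bound | 14.6 | 2.2 | 1.5 |
| | share with p < 0.05 | 57% | 93% | 92% | 90% |

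The 38 is unstable: its interquartile range runs from 3.5 to the fitting bound. The 3.2 at s = 1 is a coincidence of the settings, since the same substitute gives 14.6 when the truth is 6.

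**4. A censored alternative.** A log10 mixed model left-censored at the limit, under the same assumptions, had medians of 3.4 and 6.3 for true ratios 3 and 6, with about 7% rejections under no effect. A repeat with 300 data sets per scenario gave 2.8 and 6.3, with 9% rejections. In that repeat the interquartile ranges were 1.6 to 6.9 and 3.8 to 23. With no true effect, 24% of data sets had no quantifiable value at all.

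**5. An exact paired test of detectability.** With 5 discordant pairs all one way, two-sided p = 2 × 0.5⁵ = 0.0625; with 6, p = 2 × 0.5⁶ = 0.031. Assume one value per arm and independent arms. Power is then about 0.5% for 5% versus 21% detectable, and about 10% for 5% versus 39%.

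**The case against.** Several points on the other side stand.

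- **Substitution is not prescribed.** A reader might infer that the plan substitutes an arbitrary number. It does not say so; it is silent. The defect is that the named model cannot run without such a number and no rule supplies one.
- **Not everyone is always undetectable.** A reader might take eligibility to mean that nearly every value will be censored. Isolated values of 50-500 copies/ml are allowed, and eligibility restricts only values up to entry. After dosing, the expectation of few quantifiable values rests on the prediction in 2.1. No fraction is given.
- **It is not the powered outcome.** The heading of 14.3 might suggest that the trial's main result is at risk. CA-US RNA carries the power statement and has its own linear mixed model, and 5.1 says there is no primary efficacy endpoint. Plasma viral load is also collected for safety.
- **Significance is steadier than size.** Among positive substitutes, the share with p < 0.05 moved only between 50% and 60% at a true ratio of 3. It drops sharply at zero. The documents and these checks do not support saying that the significance result is arbitrary throughout.
- **A count model can suit plasma HIV RNA.** With a low-copy assay, a known plasma volume and an offset, it could be defended. None of these is described for plasma.

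It is also unclear whether three plasma baselines exist. Section 2.1 names only screening and baseline before dosing, and the Study Events Table is not in the supplied text. None of this removes the mismatch between model and data.

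**Conclusion.** The concern holds for the plasma HIV RNA analysis in 14.3 and no further. The model and the baseline average need a number for values that are likely to be mostly left-censored, and the estimated ratio then depends heavily on that number. At a true ratio of 3 the median estimate ran from about 1.2 to about 38. Leaving zero aside, it still ran from 1.17 to 3.2.

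These sizes rest on an assumed limit of 40 copies/ml, SDs of 0.4 log10 and about 5% of baseline values quantifiable. The direction does not depend on the limit, as the limit-free example shows. With more quantifiable values the dependence shrinks.

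This should be corrected before the data are analysed. It does not call the CA-US RNA analysis or its sample size into question.

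**What to change.** Change 14.3 as follows:

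1. State the plasma assay and its limit of quantification.
2. Replace the negative binomial model for plasma HIV RNA with a mixed model on log10 values, left-censored at that limit, with a participant random effect.
3. Enter each baseline measurement as its own, possibly censored, observation. Do not average substituted values. State how many plasma baselines there are.
4. Report the number detectable at each time point and in each arm descriptively.
5. Use substitution only as a sensitivity analysis, with the substitutes named in advance.
6. State that if the censored model cannot be estimated, only the detectability counts will be reported.

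An exact McNemar test should not be the main analysis. With 10 participants it needs at least 6 discordant pairs all in one direction, and its power is very low in the scenarios above.

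The cost is analysis wording only: no samples, visits or participants change. The downside is real. With n = 10 and few quantifiable values the censored estimate is imprecise, its likelihood-ratio test ran slightly above 5% in the simulations, and the model may not be estimable if almost nothing is quantifiable. In that last case the data hold little information about magnitude under any method.
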